3.12.5. PK Analysis Population

The PK analysis population is defined as all patients who have at least one non-missing PK concentration data point.

3.13. Data Display Characteristics

Data displays produced for this study will include summary tables, data listings, and figures.

Data listings will report the data reported in the clinical database or derived for each patient. Data will be ordered by patient number, and date/time of assessment if applicable. When expedient, additional levels of ordering hierarchy may reflect subsets of assessments within patient. Data listings will not display patient initials.

Summary tables will display summary statistics calculated for the analysis population, unless described otherwise.

The summary statistics displayed will be a function of the type of data associated with the summarized assessment. Unless stated otherwise, continuous data will be summarized with the number of non-missing values, mean, standard deviation, minimum, median, and maximum. Categorical data will be summarized with the number of non-missing values and the numbers of values equal to each of the possible values. Percentages of patients with each of the possible values will be calculated from the number of patients in the corresponding analysis population, unless stated otherwise. Some continuous variables may also be grouped into categorical levels and evaluated in frequency tables.

4. **PATIENT ACCOUNTABILITY**

4.1. Patient Characteristics

Patient characteristics will be summarized and listed for the Safety population. These summaries will also be produced for the Efficacy Evaluable population if more than 5% of patients in the Safety population are excluded from the Efficacy Evaluable population.

4.1.1. Demography

Data collected about the following patient characteristics at the screening visit will be summarized as follows:

- Age is collected in the clinical database at the time of patient registration. As this is a global study, there are certain regions where local regulations prohibit the collection of a complete date of birth. Therefore, age will not be recalculated for analysis purposes. The collected age will be used for summarization.
- Sex
 - Childbearing potential (female only, yes/no)
- Ethnicity
- Race

All demography data, including informed consent date, will be listed.

4.1.2. Baseline Height, Weight, and AIBW

Baseline height, weight, and AIBW will be summarized and presented in a listing.

4.1.3. Medical History

Medical history will be coded using Medical Dictionary for Regulatory Affairs (MedDRA) (Version 24.0) and graded using Common Terminology Criteria for Adverse Events (CTCAE) Version 5.0, associating lower-level terms with preferred terms (PTs) and system organ classes (SOCs) by the primary hierarchy. Medical histories will be summarized as the number and percentage of patients who reported at least 1 medical history event; and number and percentage of patients who reported at least 1 medical history event in each SOC. Within each SOC, tables will display the number and percentage of patients reporting at least 1 medical history event as designated by PT. All medical history information will also be listed.

4.1.4. Disease Characteristics, Prior Therapy, and Gene Mutations

Listings of all collected data related to disease characteristics and prior therapy will be provided. A summary of the following elements will also be provided:

- ECOG performance status (0/1)
- Primary diagnosis (epithelial ovarian cancer, fallopian tube cancer, primary peritoneal cancer, other)
- Histology

- Disease stage at initial diagnosis
- Histologic grade
- Prior radiotherapy (yes/no)
- Prior systemic therapy
 - The number of prior systemic therapies is defined as the number of distinct treatment regimens.
- Prior cancer related surgery (yes/no)
- Prior exposure to doxorubicin (yes/no), topotecan (yes/no), taxanes (yes/no)
- Prior exposure to PARP inhibitors (yes/no/uncertain)
 - If patient participated in a double-blind randomized trial comparing PARP inhibitor to placebo and the actual treatment was unknown, patient will be summarized under 'uncertain' category.
- Any *BRCA* mutations (yes [*BRCA1*, *BRCA2*]/no)
- Primary platinum-free interval (months, ≤ 12 months vs > 12 months)
 - Defined as time from last dose of 1st line platinum therapy to the date of disease progression and/or relapse following 1st line therapy.
- Platinum-free interval (months, ≤ 3 months vs $\geq 3-6$ months, vs ≥ 6 months)
 - Defined as time from last dose of latest line platinum therapy to the date of disease progression and/or relapse following that line of therapy.

4.2. Patient Disposition

4.2.1. Screened and Treated Patients

The number and percentage of patients who were screened, treated (Safety population), not treated (screen failure), and reason for screen failure will be summarized overall, and by geographic region, country, and site.

4.2.2. Patient Disposition

A summary of patient disposition will summarize, for the Safety population, the number of patients treated and the reason for treatment and study discontinuation. This summary will also be produced for the Efficacy Evaluable population by Investigator if more than 5% of patients in the Safety population are excluded from the Efficacy Evaluable population.

Percentage of patients who withdrew for each reason on the End-of-Treatment and End-of-Study forms will be calculated using all members of the relevant population for the denominator.

The number and percentage of Safety population included in each analysis population defined in Section 3.12 will be presented. This table will be produced for all patients at all sites, pooled.

4.2.3. Protocol Deviations and Population Inclusions

Protocol deviations will be captured in a protocol deviation log. A summary of the number of patients with any protocol deviation will be provided for the Safety population.

Major protocol deviations will also be summarized in these categories:

- Patients entered the study even though they did not satisfy the entry criteria.
- Patients received incorrect dose.
- Major deviations that affect safety and/or efficacy endpoints assessments.
- Major deviations due to Covid-19 pandemic.
- Deviations that impact the principles of ICH GCP regarding patient rights, safety, and well-being.
- Other important deviations not otherwise described that may significantly affect a subject's rights, safety, or well-being.

5. EFFICACY ANALYSES

The main efficacy analyses will use data from the Efficacy Evaluable population based on investigator's assessment. Sensitivity analyses will be performed with BICR assessment.

5.1. Efficacy Outcomes

5.1.1. Best Overall Response

Best overall response (BOR) for a patient is the best response designation as assessed by the Investigator recorded between the date of first dose of MIRV and the date of objectively documented PD per RECIST Version 1.1, the date of the start of new anti-cancer therapy, or the date of study discontinuation, whichever occurs first. When an analysis cutoff date is implemented, only radiological assessments occurring on or prior to the cutoff date will be used for analysis. Patients with an overall response of CR or PR must have a repeat tumor assessment performed no less than 4 weeks (28 days) after the criteria for response are first met. When stable disease is the best overall response, it must meet the minimum duration of 35 days (6 weeks – 1-week window = 35 days from the date of first dose of MIRV). The confirmatory scan is valid following treatment discontinuation if the patient has not started a new anti-cancer therapy.

5.1.1.1. ORR

The ORR will be calculated as the number of patients with a confirmed BOR of CR or PR divided by the number of patients in the Efficacy Evaluable population. Patients without at least 1 post-baseline RECIST assessment will be treated as non-responders (ie, these patients will contribute to the denominator, but not the numerator).

5.1.1.2. DOR

DOR is defined as the time from the date of the first response (CR or PR), whichever occurs first, to the date of PD or death from any cause, whichever occurs first. DOR is only defined for patients who have a confirmed BOR of CR or PR.

Per the BOR definition, patients with an overall response of CR or PR must have a repeat tumor assessment performed no less than 4 weeks after the criteria for response are first met. The first

date at which a CR or PR response was noted will be used to calculate DOR, not the date of the confirmatory tumor assessment.

Patients who started a new anti-cancer therapy prior to documented PD or death will be censored at the last radiological assessment prior to initiation of new anti-cancer therapy. Patients who did not have PD or death will be censored at the date of their last radiological assessment. Patients who had PD or death after missing 2 or more consecutive radiological assessments (PD or death date - last radiological assessment date $+1 \ge 105$ days) will be censored at the date of their last radiological assessment before the missing radiological assessment. When an analysis cutoff date is implemented, only data (deaths or radiological assessments) occurring on or before the cutoff date will be used for analysis.

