7.13. Tumor Response Assessment

7.13.1. Radiological Imaging

Radiologic tumor evaluation by CT or MRI of chest, abdomen, and pelvis will be performed within 28 days before first dose of study drug and every 6 weeks (± 1 week) from C1D1 for the first 36 weeks on study and every 12 weeks (± 3 weeks) thereafter (Table 2). Patients who discontinue study treatment for reasons other than progressive disease (PD) will continue with tumor assessments until documentation of PD or the start of a new anticancer therapy, whichever comes first. Prior to Week 36 (from Cycle 1, Day 1), assessments should occur every 6 weeks (± 1 week) as allowed by local requirements but must occur at an interval of no more than 12 weeks. After Week 36, assessment will occur every 12 weeks (± 3 weeks) until documentation of PD or the start of new anticancer therapy. The same method of radiographic assessment used at Screening must be used at all subsequent radiographic evaluations. Copies of all imaging scans must be obtained and sent to a central imaging vendor designated by ImmunoGen as outlined in the Imaging Manual. The central imaging vendor will assess the quality of the images. The imaging vendor will be responsible for the formation and management of the blinded independent central review (BICR) which will be used as a sensitivity analysis of ORR and DOR by investigator.

Tumor response will be assessed by the Investigator using RECIST v1.1 (Eisenhauer 2009). Response as determined by the Investigator will be recorded in the clinical trial database.

The central imaging vendor will ensure that the central radiologists remain blinded to the local assessment from the Investigator and other unblinding information. This and all other imaging procedures will be documented in an independent review charter agreed upon between ImmunoGen and the imaging vendor before initiation of any BICR reviews.

Note: It is very important that the same method of radiologic assessment be used throughout the study and that the same lesions are followed.

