10.4.2. Key Secondary Efficacy Endpoint

The key secondary endpoint of Investigator-assessed DOR will be estimated using Kaplan-Meier method for survival function estimate.

The initial analysis of DOR will be conducted at the time of primary analysis of ORR. An updated analysis of DOR will be conducted 12 months after the primary analysis of ORR, at the end of the study.

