2.1.3.3. Exploratory Endpoints

2.2. Study Overview

This study is designed to evaluate the efficacy and safety of MIRV in women with PROC and high $FR\alpha$ expression.

Eligible patients will receive MIRV 6 mg/kg AIBW Q3W until disease progression, unacceptable toxicity, withdrawal of consent, death, or until the Sponsor terminates the study (whichever comes first).

Tumor assessments, including radiological assessments by CT/MRI scans will be performed at Screening and subsequently every $6 (\pm 1)$ weeks from C1D1 for the first 36 weeks then every 12 (± 3) weeks until disease progression, death, the initiation of subsequent anticancer therapy, or patient's withdrawal of consent, whichever occurs first. CT/MRI scans will be collected for sensitivity analysis by blinded independent central review (BICR).

Patients who discontinue MIRV for reasons other than progressive disease (PD) will continue with tumor assessments until documentation of PD or the start of new anticancer therapy, whichever comes first.

All patients who discontinue MIRV will be followed for survival every 3 months (± 1 month) until death, lost to follow-up, withdrawal of consent for survival follow-up, or End of Study (EOS), whichever comes first.

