3.9. Timing of Final Analysis

To allow for reasonable duration on treatment to achieve a confirmed response, the final analysis for ORR will be conducted after all efficacy evaluable patients (defined in Section 3.12.3) have:

- undergone at least 4 post-baseline tumor assessments, or
- experienced radiological disease progression, or
- died or had clinical progression within 105 days of first dose of MIRV, or
- withdrawn from study for other reasons

It is estimated that the final analysis will be conducted approximately 6 months after the last patient is enrolled.

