5.1.2. PFS

PFS is defined as the time from the date of first dose of MIRV until the date of PD or death from any cause, whichever occurs first. PFS is defined based on radiological assessments and determined by the Investigator. Clinical progression is not considered a progression endpoint.

Table 3 summarizes the rules to be used for PFS. When an analysis cutoff date is implemented, only data (deaths and radiological assessments) occurring on or prior to the cutoff date will be used for analysis.

Situation	Date of PFS ^a Event or Censoring	Outcome
No post-baseline radiological assessments, and patient did not die within 105 days of first dose	Date of first dose	Censored
No post-baseline radiological assessments, and patient died within 105 days of first dose	Date of death	Death
Death	Date of death	Death
Radiological Progression	Date of first radiological assessment indicating progression (ie, OR = PD).	Progression
New anti-cancer therapy prior to PD or death (including palliative radiotherapy during study treatment)	Date of last radiological assessment prior to the start of the new anticancer therapy	Censored
No death or PD	Date of last radiological assessment	Censored
PD or death after missing 2 or more consecutive radiological assessments (PD or death date - last radiological assessment date $+1 \ge 105$ days)	Date of last adequate radiological assessment showing no PD	Censored

Table 3:PFS Definitions

Abbreviations: OR = overall response; PD = disease progression; PFS = progression-free survival.

^a Includes radiographic progression only.

5.1.3. OS

OS is defined as the time from the date of first dose until the date of death from any cause.

Patients who are alive or lost to follow-up at the analysis are censored at the last known date at which they were known to be alive. When an analysis cutoff date is implemented, only deaths occurring on or before the cutoff date are counted as OS events. Patients whose date of death or the last date at which the patient was known to be alive (eg, after the data cutoff date) will be censored at the analysis cutoff date.

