5.3. Secondary Efficacy Analyses

5.3.1. Key Secondary Efficacy Analysis

The key secondary endpoint of DOR will be summarized in patients with a confirmed BOR of CR or PR only.

The distribution of DOR will be summarized using the Kaplan-Meier method. DOR rates will be reported at 3-month intervals (eg, 3 months, 6 months, etc.). Median DOR will be estimated from the 50th percentile of the corresponding Kaplan-Meier estimates. 95% CIs for the 3-month intervals and median DOR will also be provided.

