5.5. Additional Sensitivity Analyses

Analysis of ORR, DOR, and PFS as assessed by BICR will be performed as sensitivity analysis using the same methods described in the previous sections.

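### The SAP's single 105-day rule for two missed scans fits only the 6-weekly schedule; after Week 36 it also censors progressions after one missed scan or none, which raises late DOR rates.

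*SAP*

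**What the plan says.** SAP 5.1.1.2 censors DOR at the last scan before the gap for "Patients who had PD or death after missing 2 or more consecutive radiological assessments (PD or death date - last radiological assessment date", plus 1, is at least 105 days. SAP 5.1.2, Table 3, applies the same 105 days to PFS for "PD or death after missing 2 or more consecutive radiological assessments".

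The scan interval changes during the trial. SAP 2.2 has scans every 6 (±1) "weeks from C1D1 for the first 36 weeks then every 12" (±3) weeks. Protocol 7.13.1 agrees: every 6 weeks (±1 week) "from C1D1 for the first 36 weeks on study and every 12 weeks" (±3 weeks) thereafter. Neither document gives a different day count for the 12-weekly period.

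SAP 5.3.1 says "DOR rates will be reported at 3-month intervals". Protocol 10.4.2 says "An updated analysis of DOR will be conducted 12 months after the primary analysis of ORR". SAP 5.5 repeats ORR, DOR and PFS on BICR data "using the same methods described in the previous sections", so those analyses carry the same rule.

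**The concern.** The rule is worded as a count of missed scans but calculated as one fixed number of days. Once the interval doubles, the same number of days means fewer missed scans. A progression found after a single missed 12-weekly scan, or at a late but in-window scan with none missed, becomes a censored observation although the wording would count it as an event.

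The later part of the DOR curve is where this falls. By the updated analysis, the late events come from 12-weekly scans. There is no control arm in which the same distortion would appear, and the BICR analyses would reproduce it. No planned analysis relaxes the rule, so nothing in the tables would reveal it.

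**Working it through.** **Inputs from the documents.** Threshold: date difference + 1 ≥ 105, that is, a gap of 104 days or more. Windows: ±7 days to Week 36, ±21 days after. Follow-up: the Protocol Synopsis gives about 30 months in total, SAP 3.9 says "the final analysis will be conducted approximately 6 months after the last patient is enrolled", and the end of study is 12 months after that. Enrolment is therefore about 30 − 6 − 12 = 12 months, and follow-up at the updated DOR analysis is 18–30 months. Responders: 105 × 24% ≈ 25 (design alternative) to 105 × 31.4% ≈ 33 (earlier eligible patients, Protocol 10.5).

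**1. Where 105 comes from.** Gap = planned distance ± the sum of the two windows. On the 6-weekly schedule:
- none missed: 42 ± 14 = 28–56 days
- one missed: 84 ± 14 = 70–98 days
- two missed: 126 ± 14 = 112–140 days

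The midpoint of 98 and 112 is 105, so the rule separates one from two missed scans exactly.

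**2. The same arithmetic from Week 36.**

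| Last scan → PD scan | Missed | Gap (days) | Censored? |
|---|---|---|---|
| Week 36 → 48 | 0 | 84 ± 28 = 56–112 | some |
| Week 48 → 60 | 0 | 84 ± 42 = 42–126 | some |
| Week 30 → 48 | 1 | 126 ± 28 = 98–154 | nearly all |
| Week 36 → 60 | 1 | 168 ± 28 = 140–196 | all |
| Week 48 → 72 | 1 | 168 ± 42 = 126–210 | all |
| Week 48 → 84 | 2 | 252 ± 42 = 210–294 | all (as intended) |

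**3. Share censored, if every whole day in a window is equally likely (assumption).**
- Week 36 → 48: 15 × 43 = 645 date pairs. The second deviation must exceed the first by at least 20 days: 9 + 8 + … + 1 = 45 pairs, 7.0%.
- Week 48 → 60: 43 × 43 = 1,849 pairs; 23 + 22 + … + 1 = 276, 14.9%.
- Week 30 → 48: 1 + 2 + … + 6 = 21 of 645 pairs escape, so 96.7% are censored.

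If scan days cluster around the nominal date (normal, SD one third of the half-window), the shares are 0.4%, 2.4% and 99.9%. At nominal dates the no-miss gap is 84 days and nothing is censored. A nominal scan followed by one 21 days late gives 105 days, which is censored.

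**4. Effect on the updated DOR analysis.** Simulation of 200,000 responders per scenario. Assumptions: exponential DOR with median 5.7 or 7.8 months (both quoted in the protocol); response at Week 6 or 12; scan days uniform, clustered or nominal; 0, 10 or 20% of scans missed; no deaths and no new therapy. Differences are the 105-day formula minus a rule that censors only after two or more consecutive missed scheduled scans.

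| Scans missed | Post-Week-36 PDs wrongly censored | Events in 25–33 responders | 12-month rate (points) | 15-month rate (points) |
|---|---|---|---|---|
| 0% | 0–15% | 0–2 | 0 to +1.7 | 0 to +2.5 |
| 10% | 17–29% | 1.5–4 | +0.3 to +3.3 | +1.3 to +4.8 |
| 20% | 26–36% | 2.5–5 | +0.6 to +4.8 | +2.5 to +7.2 |

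At 0–10% missed, the 9-month rate moves by −0.6 to +0.9 points. It can dip because a patient censored early leaves the risk set before the date of the discarded event; from that date on, the curve is higher. The median moves by 0.1 month or less in 21 of the 24 scenarios with 0–10% missed. In the other 3 it jumps by 0.3–2.8 months because the curve sits near 50% between scans. A second simulation with somewhat different assumptions (0–15% missed) gave 0 to +2.7 points at 12 months and 0 to +5.2 at 15.

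At the first DOR analysis about one event at most is affected. For PFS (medians 4.8 and 6.7 months, 0–10% missed) the median is unchanged, and the 15-month rate moves by 0 to +2.3 points.

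**5. Scale.** The 95% half-width for a 40% rate is 1.96 × √(0.4 × 0.6/25) = 19 points with 25 responders and 17 with 33.

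**The case against.** The sponsor could say that the words govern and the bracketed formula only illustrates them. The censoring date, defined as the last scan before a missing one, presupposes that a scan was missed. On that reading the no-miss cases would not be censored. This is arguable, but a program needs a rule, the formula is the only computable one given, and the documents do not say which prevails.

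The size rests on inputs that the documents do not supply. The upper figures need scan days spread evenly over a 6-week window, or 20% of scans missed. The simulation also leaves out deaths and new therapy. Deaths or unscheduled scans soon after one missed scan can fall below the cut-off. These limits stand, which is why ranges are given and zero is among them.

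The comparison is with a count of missed scans, not with the true curve. Dating progression at 12-weekly scans raises the rate by itself: with a true median of 7.8 months the true 12-month rate is 0.5^(12/7.8) = 34%, while the counting rule gives about 41–42% (response at Week 6, no scans missed). That is larger than the formula's effect, but it comes from the schedule. The formula's error is added to it and can be avoided.

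Finally, ORR is untouched, SAP 3.11.2 plans no formal test of DOR or PFS, and SAP 5.6 lists the censoring, so affected patients could be found afterwards. This limits the severity but does not make the formula match its wording.

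**Conclusion.** The concern holds. The 105-day formula contradicts the SAP's own wording once scans become 12-weekly. The gap arithmetic follows from the documents alone: every in-window progression after one missed 12-weekly scan is censored, as are nearly all when only Week 36 is missed and some when no scan is missed.

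DOR rates at 12 months and later are biased upward relative to the stated rule, by nothing at best and by a few points under plausible non-attendance. Earlier rates move slightly in either direction, and the median usually does not move. The bias is well inside sampling error and does not touch the primary test. It should still be fixed, because it is a systematic error in the key secondary endpoint that no planned analysis would show.

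**What to change.** In SAP 5.1.1.2 and Table 3, define the condition by counting missed scheduled assessment windows, and apply it to the BICR analyses as well.

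If a day rule is preferred, make it depend on the last scan, with the +1 included:
- **Week 24 or earlier, 105 days:** one missed gives at most 99, two missed at least 113.
- **Week 30, 168 days:** one missed gives at most 155, two missed at least 183.
- **Week 36 or later, 212 days:** one missed gives at most 211. A 210-day cut-off would still catch some single misses. With 212, the only in-window two-miss gap that escapes is one of exactly 210 days: 1 of 1,849 date pairs, 0.05%.

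The day rule can still misplace a few deaths that fall between scans; counting windows avoids that.

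Add a DOR and PFS sensitivity analysis that counts every PD and death as an event regardless of missed scans.

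Separately, and not included in the figures above, Protocol Table 2 footnote m gives two different off-treatment scan intervals before Week 36: 12 ± 3 weeks, and 6 weeks with no more than 12. These must be reconciled so that missed windows can be counted for those patients.

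The cost is a wording change and one derivation, with no new data; SAP 1.1 allows changes before final database lock. Late DOR rates may be reported a few points lower.
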